# 4.3.2 Maximum Dose/Exposure for This Study

For a given participant, the maximum planned dose of POS is 300 mg per administration (administered BID on Day 1 and QD on subsequent days for a maximum of 84 days). Participants who weigh >40 kg will receive the maximum planned dose of 300 mg. The maximum total daily dosing established for this study reflects the approved dose for POS solid oral tablet and POS IV solution formulations, which is 300 mg BID on Day 1 followed by 300 mg QD.

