#### 4.3 Justification for Dose

#### 4.3.1 Starting Dose for This Study

All randomized participants will begin study dosing with the IV formulation of POS. The dose of 6 mg/kg/day for the IV formulation was chosen for this study based on the results of the Phase 1B PK and safety study of POS in children and adolescents (P097) as well as the approved dosing of POS IV for children 2 years of age and older. Participants will receive POS IV at a dose of 6 mg/kg/day BID on Day 1 and QD thereafter.

After at least 7 days and when clinically appropriate, participants can be switched to an oral formulation. Participants weighing  $\leq$ 40 kg will transition to the PFS formulation. The dosing for the PFS formulation, shown in Table 1, reflects the approved pediatric weight-based dosing of this formulation and reflects the approved labeled dosing of this formulation. Weight-band dosing is expected to provide POS exposures similar to that previously

specified in the protocol before implementation of this amendment. Participants weighing >40 kg will transition to the tablet at a dose of 300 mg. The choice of 40 kg as the weight to transition to a 300-mg tablet dose aligns with the pediatric dosing of the tablet in approved product labeling for POS tablet. The dosing of the tablet also reflects the approved dosing of POS tablet as shown in product labeling for the treatment of IA.

Weight (kg)	PFS Dose (volume)
10-<12 kg	90 mg (3 mL)
12-<17 kg	120 mg (4 mL)
17-<21 kg	150 mg (5 mL)
21-<26 kg	180 mg (6 mL)
26-<36 kg	210 mg (7 mL)
36-40 kg	240 mg (8 mL)
PFS= powder for delayed release oral suspension	

Table 1 Dosing of the PFS

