# Table 3Study Treatments

Arm Name	Arm Type	Intervention Name	Intervention Type	Dose Formu- lation	Unit Dose Strength(s)	Dosage Level(s)	Route of Adminis- tration	Regimen/ Treatment Period	Use	IMP or NIMP/AxMP	Sourcing
Posaconazole	Experi- mental	IV	Drug	Vial	18 mg/mL	6 mg/kg Doses are not to exceed 300 mg per administration	IV Infusion	Day 1: BID Day 2 through end of IV dosing: QD	Test Product	IMP	Centrally sourced with the ability to source locally if required
Posaconazole	Experi- mental	Powder for suspension (PFS)	Drug	Powder for Suspension	30 mg/mL	Dosing based on weight-band. To be administered to participants ≤40 kg	Oral	Days 8 – 84: QD	Test Product	IMP	Centrally sourced with the ability to source locally if required
Posaconazole	Experi- mental	Tablet	Drug	Tablet	100 mg	300 mg To be administered to participants >40 kg	Oral	Days 8 – 84: QD	Test Product	IMP	Centrally sourced with the ability to source locally if required

Abbreviations: AxMP Auxiliary Medical Product, EEA=European Economic Area, IMP= Investigational medical product, NIMP=non-investigational medical product, QD= Once daily

The classification of Investigational Medicinal Product (IMP) and Non-Investigational Medicinal Product (NIMP) in this table is based on guidance issued by the European Commission and applies to countries in the European Economic Area (EEA). Country differences with respect to the definition/classification of IMP/NIMP may exist. In these circumstances, local legislation is followed.

All supplies indicated in Table 3 will be provided per the "Sourcing" column depending upon local country operational requirements. If local sourcing, every attempt should be made to source these supplies from a single lot/batch number where possible (eg, not applicable in the case where multiple lots or batches may be required due to the length of the study, etc).

Refer to Section 8.1.8 for details regarding administration of the study intervention.

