# 6.2 Preparation/Handling/Storage/Accountability

## 6.2.1 Dose Preparation

The rationale for the selection of doses to be used in this study is provided in Section 4.3, Justification for Dose.

The participant's body weight at Day 1 will be used to calculate the dose of POS IV study treatment. The participant's body weight as measured within 3 days before the first day of oral POS treatment will be used to calculate all subsequent doses of oral POS: any participant whose weight is  $\leq$ 40 kg will transition to the PFS formulation; any participant whose weight is >40 kg will transition to the tablet formulation and will receive 300 mg as 3 × 100-mg tablets. For any subsequent switch from oral to IV formulation, the IV dose will be calculated based on the participant's weight before the initial switch to an oral formulation.

Instructions for preparation of the IV infusion and the PFS oral solution are found in the Pharmacy Manual. Instructions for administration of PFS will be provided to caregivers separately.

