# 8.3.1 Physical Examinations

A complete physical examination will be conducted by an investigator or medically qualified designee (consistent with local requirements) as per institutional standard. The complete physical examination includes the following assessments: general appearance, head, eyes, ears/nose/throat, neck, lymph nodes, skin, lungs, heart, abdomen, musculoskeletal, and neurologic evaluations. Breast, rectal, and genitourinary/pelvic exams should be performed when clinically indicated.

Height and weight will also be measured and recorded. Height measurements should be taken without shoes and be recorded to the nearest cm. Body weight at baseline will be used to calculate the participant's dose for the IV treatment phase of the study. The participant's weight measured within 3 days before the first dose of oral treatment should be used to calculate all subsequent doses of the PFS oral formulation, as well doses of the IV formulation. Body

weight should be obtained without shoes. At each required visit, it is preferred that the weight be measured on the same scale for the same individual. Measurements should be recorded to the nearest 0.1 kg.

A brief directed physical examination will be conducted by an investigator or medically qualified designee (consistent with local requirements) per institutional standard at any other visit when clinically indicated.

Investigators should pay special attention to clinical signs related to previous serious illnesses.

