# 8.5 Treatment of Overdose

In this study, an overdose is any dose higher than the protocol-specified dose as provided in Section 6.1.

Decisions regarding dose interruptions or modifications will be made by the investigator in consultation with the Sponsor's Clinical Director based on the clinical evaluation of the participant.

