# 8.9.2.2 Treatment Period

All participants will initiate treatment with IV POS and may transition to oral POS after a minimum of 7 days on IV study treatment, as clinically indicated. Dosing selection and preparation are described in Section 4.3 and Section 6.2, respectively. Study visits in the treatment period will occur at Day 3 and Weeks 1, 2, 4, 6, 9 and 12. At these scheduled visits, procedures/assessments are to be performed according to the SoA.

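### Section 4.3.2 gives 300 mg to everyone above 40 kg without naming a formulation, which conflicts with the 6 mg/kg IV rule in Table 3 for children above 40 kg and below 50 kg

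*Combined protocol and SAP*

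**What the plan says.** Section 4.3.2 opens with the ceiling: no more than 300 mg at each administration, given twice on Day 1 and once daily afterwards, for up to 84 days. It continues: "Participants who weigh >40 kg will receive the maximum planned dose of 300 mg". The section's last sentence ties the maximum to the approved dose of both the solid tablet and the IV solution.

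The dosing rules elsewhere differ by formulation:

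- **IV.** Table 3 (Section 6.1) gives "6 mg/kg Doses are not to exceed 300 mg per administration". Section 6.2.1 adds: "The participant's body weight at Day 1 will be used to calculate the dose of POS IV study treatment". The synopsis has the same 6 mg/kg rule and the same ceiling.
- **Tablet.** Section 4.3.1 says: "Participants weighing >40 kg will transition to the tablet at a dose of 300 mg". Table 3 and Section 6.2.1 agree.

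Two other places bear on how the sentence would be used. Section 8.9.2.2 tells sites: "Dosing selection and preparation are described in Section 4.3 and Section 6.2, respectively". Section 8.5 says that "an overdose is any dose higher than the protocol-specified dose as provided in Section 6.1".

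**The concern.** The sentence in Section 4.3.2 is a categorical dosing statement with no formulation attached, and its surroundings do not confine it to the tablet. The twice-daily Day 1 schedule in the sentence before it applies only to IV, since oral dosing is once daily from Day 8. The sentence after it names the IV solution. Read as written, it sets a flat 300 mg IV dose above 40 kg, whereas Table 3 makes the IV dose proportional to weight until the ceiling is reached.

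The stakes are in dosing rather than analysis. All participants begin on IV and stay on it for at least 7 days. The first oral switch may come as late as the Week 9 visit, and returns to IV are allowed (Section 4.1). Sites are directed to Section 4.3 for dosing selection. Within it, Section 4.3.1 gives the 6 mg/kg IV dose but no ceiling, so a reader looking for the IV ceiling there finds it only in Section 4.3.2, next to the sentence in question. A site that applied that sentence to IV would give a dose that Section 8.5 treats as an overdose, reportable within 5 calendar days under Table 7. One section would then be prescribing what another classes as an overdose.

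**Working it through.** **Inputs**

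- IV rule: 6 mg/kg, at most 300 mg per administration (Table 3), from Day 1 weight (Section 6.2.1).
- Tablet rule: flat 300 mg above 40 kg (Section 4.3.1, Table 3).
- Figure under test: 300 mg for anyone above 40 kg (Section 4.3.2).
- Weight precision: "Measurements should be recorded to the nearest 0.1 kg" (Section 8.3.1), so the lowest recordable weight above 40 kg is 40.1 kg and the highest below 50 kg is 49.9 kg.
- Minimum IV course: 7 days, with two doses on Day 1 and one on each of the next six days, so 2 + 6 = 8 doses.

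**Step 1: where 300 mg reproduces.** For the tablet, it reproduces at every weight above 40 kg. For IV, the dose is min(300, 6 × weight), and the ceiling is reached at 300/6 = 50 kg. So 300 mg also reproduces for IV at 50 kg and above.

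**Step 2: where it does not.** For IV above 40 kg and below 50 kg, 6 × weight is less than 300 mg. The relative excess from giving 300 mg is 300/(6 × weight) − 1.

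| Weight (kg) | IV dose per Table 3 (mg) | Excess if 300 mg given (mg) | Excess (%) | mg/kg at 300 mg |
|---|---|---|---|---|
| 40.1 | 240.6 | 59.4 | 24.7 | 7.48 |
| 41 | 246 | 54 | 22.0 | 7.32 |
| 45 | 270 | 30 | 11.1 | 6.67 |
| 48 | 288 | 12 | 4.2 | 6.25 |
| 49 | 294 | 6 | 2.0 | 6.12 |
| 49.9 | 299.4 | 0.6 | 0.2 | 6.01 |
| 50 | 300 | 0 | 0.0 | 6.00 |

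**Step 3: accumulated excess.**

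- Day 1 at 40.1 kg: 2 × 240.6 = 481.2 mg due against 2 × 300 = 600 mg, an excess of 118.8 mg.
- Minimum 7-day IV course at 40.1 kg: 8 × 59.4 = 475.2 mg.
- Minimum 7-day IV course at 45 kg: 8 × 30 = 240 mg.

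**Step 4: returning to IV.** Section 6.2.1 also makes the IV dose after an oral period weight-based. A 45 kg child on the 300 mg tablet should return to 270 mg IV; Section 4.3.2 read literally gives 300 mg.

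**The case against.** The best defence is that context supplies the missing word. Everywhere else that 40 kg appears as a dosing threshold (synopsis, Sections 4.3.1, 4.3.3 and 6.2.1, Table 3) it selects the oral formulation, and no other text applies it to IV. Section 4.3.2 is dose justification; Section 4.1 sends readers to Section 6.1 for doses, and Table 3 there is clear. A site following Section 8.9.2.2 would meet a mg/kg IV dose in Section 4.3.1 and a weight-based IV calculation in Section 6.2.1, on either side of the disputed sentence. The 24.7% figure belongs to the bottom of the band and arises only if a site makes the error. Preparation instructions are in the Pharmacy Manual, which is not among the documents reviewed.

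Most of this stands. The tablet was probably what was meant, Table 3 governs, and most sites would probably dose from it. It is also fair to call this an inconsistency between sections rather than a miscalculation. The agreement among the dosing texts should be stated with care: the synopsis, Table 3 and Section 6.2.1 support it, Section 4.3.1 gives 6 mg/kg but no ceiling, and the schema figure is not reproduced in the text available here, so it is not relied on.

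What does not follow is that the sentence is harmless. Its neighbours refer to IV, sites are pointed to its parent section for dose selection, and it states a dose that would count as an overdose.

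**Conclusion.** The concern holds. The sentence is correct for the tablet and for IV at 50 kg and above, and wrong as written for IV above 40 kg and below 50 kg. If it were applied to IV, the dose would be above Table 3 by 24.7% at 40.1 kg, falling to 0.2% at 49.9 kg.

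That size assumes a site follows Section 4.3.2 instead of Table 3; the documents do not show how likely that is. They also give no weight distribution, so the number of participants in the band cannot be stated.

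The effect is confined to dosing clarity and safety reporting. The 300 mg ceiling is not exceeded, the overdose definition is tied to Section 6.1 and does not change, and the planned analyses are unaffected, with PK modelling based on the dose actually given (Section 9.6.2). It should be corrected, but it does not call the design into question.

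**What to change.** Replace the sentence in Section 4.3.2 with wording such as: *Above 40 kg the tablet dose is 300 mg; the IV dose remains 6 mg/kg and reaches the 300 mg maximum only at 50 kg and above.*

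Table 3 and Section 8.5 need no change. The cost is a one-sentence protocol correction, with no effect on design, endpoints or analysis.

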# 4.3.3 Rationale for Dose Interval and Study Design

In this study, all participants will initiate treatment with IV POS and may transition to oral POS after a minimum of 7 days on IV study treatment and as clinically indicated. Participants who weigh >40 kg will transition to the tablet as the oral formulation; participants who weigh  $\leq$ 40 kg and are able to transition to an oral formulation will transition to PFS. Both IV and oral treatments have been used to treat IA and other IFIs in controlled studies of IA as well as in uncontrolled studies and in salvage therapy studies [Walsh, T. J., et al 2007] [Lehrnbecher, T., et al 2010] [Conant, M. M., et al 2015] [Jeong, W., et al 2016]. Consistent with the POS (NOXAFIL) label, POS is administered twice on the first day of study treatment and then QD for the duration of treatment.

The planned duration of study treatment is 6 to 12 weeks (42 to 84 days); this aligns with current recommendations for the treatment of IA, which call for a minimum duration of treatment of 6 to 12 weeks [Patterson, T. F., et al 2016].

In this study, participants with possible IA will begin study treatment before their diagnosis of IA is confirmed. Early initiation of antifungal treatment while the definitive diagnostic evaluation is in progress is recommended by current guidelines [Patterson, T. F., et al 2016].

# 4.4 Beginning and End of Study Definition

The overall study begins when the first participant (or their legally acceptable representative) provides documented informed consent/assent. The overall study ends when the last participant completes the last study-related contact, withdraws consent, or is lost to follow-up (ie, the participant is unable to be contacted by the investigator).

For the purposes of analysis and reporting, the overall study ends when the Sponsor receives the last laboratory result or at the time of final contact with the last participant, whichever comes last. If the study includes countries in the EEA, the local start of the study in the EEA is defined as First Site Ready in any Member State.

# 4.4.1 Clinical Criteria for Early Study Termination

The clinical study may be terminated early if the extent (incidence and/or severity) of emerging effects/clinical endpoints is such that the risk/benefit ratio to the study population as a whole is unacceptable. In addition, further recruitment in the study or at (a) particular study site(s) may be stopped due to insufficient compliance with the protocol, GCP and/or other applicable regulatory requirements, procedure-related problems or the number of discontinuations for administrative reasons is too high.

# 5 STUDY POPULATION

As stated in the Code of Conduct for Clinical Trials (Appendix 1), our studies include people of varying age, race, ethnicity, and sex. The collection and use of these demographic data are to follow all local laws and guidelines in keeping with the needs for participant confidentiality while supporting the study of the disease, its related factors, and the IMP under investigation.

Male/female participants with a diagnosis of possible, probable, or proven IA aged 2 to <18 years will be enrolled in this study.

Prospective approval of protocol deviations to recruitment and enrollment criteria, also known as protocol waivers or exemptions, is not permitted.

#### 5.1 Inclusion Criteria

A participant will be eligible for inclusion in the study if the participant:

#### Type of Participant and Disease Characteristics

1. Has a diagnosis of possible, probable, or proven IA per 2020 European Organization for Research and Treatment of Cancer/Mycoses Study Group (EORTC/MSG) disease definitions (Appendix 9).

- 2. If enrolled with a possible or probable IA diagnosis, has one or more of the following risks as per 2020 EORTC/MSG disease definitions (Appendix 9).
  - Recent history of neutropenia ( $<0.5 \times 10^9$  neutrophils/L [<500 neutrophils/mm^3]) (within 30 days before screening).
  - Receipt of an allogeneic HSCT.
  - Receipt of a solid organ transplant.
  - Hematologic malignancy currently under treatment or has been treated in the recent past.
  - $\circ$  Treatment with other recognized T-cell immunosuppressants, such as calcineurin inhibitors, TNF- $\alpha$  blockers, specific monoclonal antibodies (such as alemtuzumab), or nucleoside analogues during the past 90 days.
  - Prolonged use corticosteroids for  $\geq 3$  weeks in the past 60 days (average minimum dose of  $\geq 0.3$  mg/kg/day of prednisone equivalent).
  - Congenital or inherited severe immunodeficiency (including, but not limited to chronic granulomatous disease, STAT 3 deficiency, CARD9 deficiency, STAT-1 gain of function, or severe combined immunodeficiency).
  - Treatment with recognized B-cell immunosuppressants, such as Bruton's tyrosine kinase inhibitors, eg, ibrutinib.
  - Acute graft-versus-host disease grade III or IV involving the gut, lungs, or liver that is refractory to first-line treatment with steroids.
- 3. If enrolled with a possible or probable IA diagnosis, meets mycologic and clinical criteria as per 2020 EORTC/MSG disease definitions (Appendix 9).
  - Possible IA includes participants with clinical criteria, with the anticipation that further diagnostic workup is in progress as clinically feasible and may result in updated classification of the invasive fungal infection as per the 2020 EORTC/MSG disease definitions (Appendix 9).
  - Probable IA includes participants with clinical criteria, along with mycological criteria including serum, plasma, CSF, or BAL fluid *Aspergillus* galactomannan antigen, or *Aspergillus* PCR test positive in plasma, serum, whole blood, or BAL fluid, or evidence of *Aspergillus* by histology or microscopy, or positive culture of a specimen taken by nonsterile sampling of an infected site as per 2020 EORTC/MSG disease definitions (Appendix 9).

- 4. If enrolled with a proven IA diagnosis, has demonstrated fungal elements (by cytology, microscopy, or histopathology, including *Aspergillus* nucleic acid probe where available) or positive culture for *Aspergillus* of a tissue specimen obtained from an otherwise sterile site as per 2020 EORTC/MSG disease definitions (Appendix 9).
- 5. Has a central line (eg, central venous catheter, peripherally inserted central catheter) in place or planned to be in place before beginning IV study treatment.
- 6. Has clinical symptoms consistent with an acute episode of IA, defined as duration of clinical syndrome of <30 days.

## Demographics

7. Is male or female, and  $\geq 2$  years of age and < 18 years of age at the time of first dose of study treatment and weighs at least 10 kg. Participants may be of any race/ethnicity.

## Male Participants

Contraceptive use by males should be consistent with local regulations regarding the methods of contraception for those participating in clinical studies.

- 8. Male participants are eligible to participate if they agree to the following during the intervention period and for at least 30 days after the last dose of study treatment:
- Be abstinent from heterosexual intercourse as their preferred and usual lifestyle (abstinent on a long term and persistent basis) and agree to remain abstinent

OR

- Must agree to use contraception unless confirmed to be azoospermic (vasectomized or secondary to medical cause Appendix 5) as detailed below:
  - Agree to use a male condom plus partner use of an additional contraceptive method when having penile-vaginal intercourse with a female of childbearing potential who is not currently pregnant. Note: Males with a pregnant or breastfeeding partner must agree to remain abstinent from penile-vaginal intercourse or use a male condom during each episode of penile-vaginal penetration.

#### **Female Participants**

Contraceptive use by females should be consistent with local regulations regarding the methods of contraception for those participating in clinical studies.

- 9. A female participant is eligible to participate if she is not pregnant or breastfeeding, and at least one of the following conditions applies:
  - Is not a female of childbearing potential

OR

- Is a female of childbearing potential and using a contraceptive method that is highly effective (with a failure rate of <1% per year), with low user dependency, or be abstinent from heterosexual intercourse as their preferred and usual lifestyle (abstinent on a long term and persistent basis), as described in Appendix 5 during the intervention period and for at least 30 days after the last dose of study intervention. The investigator should evaluate the potential for contraceptive method failure (ie, noncompliance, recently initiated) in relationship to the first dose of study intervention.
- A female of childbearing potential must have a negative highly sensitive pregnancy test (urine or serum as required by local regulations) within 24 hours before the first dose of study intervention.
- Additional requirements for pregnancy testing during and after study intervention are located in Appendix 2.
- The investigator is responsible for review of medical history, menstrual history, and recent sexual activity to decrease the risk for inclusion of a female with an early undetected pregnancy.

